5.4.1.3 Criteria for Assessing Severity

The Investigator will evaluate the comments of the subject and the response to treatment in order that he or she may judge the true nature and severity of the AE. Severity refers to the accumulated intensity of discomfort/impairment of health since the last recording of AEs and will be assessed according to the following criteria:

- **Mild:** Awareness of sign, symptom, or event, but easily tolerated
- **Moderate:** Discomfort enough to interfere with usual activity and may warrant intervention
- **Severe:** Incapacitating with inability to do usual activities or significantly affects clinical status and warrants intervention

The criteria for assessing severity are different from those used for seriousness.

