AEs with incomplete information for start or stop dates (i.e., either day or month is missing) will be considered treatment-emergent (TEAE) unless the partial start date or the stop date confirms the AE started or ended prior to Study Day 1 (e.g., the day of the AE start date is unknown but the month and year indicate that the AE starts prior to Study Day 1). AEs with missing relationship to study drug will be included in the “Related” category for the summary tables (Section 7.8.1). AEs with missing severity will not be included in the summary table but will be footnoted.

When there is incomplete information regarding dosing dates for prior and concomitant medication, the medication will be considered as a concomitant medication unless it contradicts with the stop date. For example, a medication will be considered a prior medication if the month and year of the end date indicates a date before Study Day 1 even though the start date could be missing.

6.5 *Interim Analysis and Adaptive Design*

The sample size estimation described in Section 3.5 is based on the effect size assumptions from the Phase 2 data in which the primary endpoint was the change from baseline to endpoint in R-MOAS ratings. However, the primary endpoint for this study is percent change in the frequency of IA incidence per 7 days in the treatment period (PCH_T) relative to the Baseline period in the ITT population. Hence, there is uncertainty as to what magnitude of alternative hypothesis

treatment difference and between-subject variability is appropriate for the sample size calculation. To this end, a single interim analysis is planned after approximately 50% of subjects complete the study for the purpose of the Stage 2 sample size adjustment.

6.5.1 *Objective*

The primary objective of this Interim Analysis is to re-evaluate the pre-specified power and sample size to consider sample size adjustment using adaptive statistical methods.

6.5.2 *Responsible Party*

This interim analysis will be performed by an independent unblinded statistician who is not affiliated to the trial sponsor, trial management, data cleaning, and analysis.

The Senior Director of Biostatistics and Executive VP and Chief Medical Officer for Clinical Developmen at Supernus (sponsor) will receive recommendation letter from the independent unblinded statistician. They will make the final decision for the sample size adjustment.

6.5.3 *Confidentiality*

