7.8.1 Adverse Events

AEs will be summarized using subject incidence table by treatment period (titration, maintenance, combined titration and maintenance, and tapering). An overview of TEAE will be presented. This table will include numbers and percentages of subjects experiencing at least 1 TEAE, study drug-related TEAE, AE leading to study drug discontinuation, severe TEAE, serious TEAE, related TESAE, AESI, and TEAE with outcome of death (Table 14.3.1.1).

Additionally, the number and percent (%) are calculated based on the number of unique subjects within each category (e.g., preferred term) by treatment group. A subject reporting multiple events of the same category will be counted only once for that category. For summary purpose, AE relationship to the study drug will be grouped into “Unrelated” for “unrelated” or “unlikely related” and “Related” for “possibly”, “probably”, or “definitely related”. For subjects with more than one event coded to the same PT, the subjects will be counted for the categories with the strongest relationship and the greatest severity. The following subject incidence tables will be presented.

- TEAEs by PT (Preferred Term) sorted by the decreasing order of subject incidence in the combined active dose group (Table 14.3.1.2.1 – Table 14.3.1.2.3)
- TEAEs by SOC (System Organ Class) and PT sorted alphabetically (Table 14.3.1.3.1 – Table 14.3.1.3.3)
- Study Drug-Related TEAEs by SOC and PT (Table 14.3.1.4.1 – Table 14.3.1.4.3)
- Severity of TEAEs by SOC and PT (Table 14.3.1.5.1 – Table 14.3.1.5.3)
- TESAEs by SOC and PT when applicable (Table 14.3.1.6)

- Number and percent of patients reporting common AEs ($\geq 5\%$ in any group) by PT (Table 14.3.1.7.1 – Table 14.3.1.7.3)
- TEAEs leading to study drug discontinuation by SOC and PT (Table 14.3.1.8)
- Treatment Emergent AESI by SOC and PT (Table 14.3.1.9)

Where warranted by the subject incidence, these same tables may be presented by treatment period (Titration, Maintenance and Conversion/Tapering).

A subject data listing will be provided for all adverse events (Listing 16.2.3.1.1). Included in the listing are the reported term, PT, SOC, TEAE flag, study day when AE starts, duration, relationship, severity, action taken, outcome, and seriousness category.

Data listings will be provided for subjects who die on study, experience SAEs, have TEAEs leading to study drug discontinuation, or AEs of special interest (Listing 16.2.3.1.2 – Listing 16.2.3.1.5).

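### Adverse events with missing severity are left out of the severity summary, so the severe count can be exact or too low but never too high

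*SAP*

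**What the plan says.** SAP 6.4 gives three rules for incomplete adverse event records, in one paragraph:

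- **Dates.** An event with a partial start or stop date "will be considered treatment-emergent (TEAE) unless the partial start date or the stop date confirms the AE started or ended prior to Study Day 1".
- **Causality.** "AEs with missing relationship to study drug will be included in the" related category of the summary tables.
- **Severity.** "AEs with missing severity will not be included in the summary table but will be footnoted".

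SAP 7.8.1 plans the displays that use the grade. There is a set of tables by organ class, preferred term and severity (14.3.1.5.1 to 14.3.1.5.3), and the overview, Table 14.3.1.1, has a line for severe TEAEs. Where a child has several events of one preferred term, "the subjects will be counted for the categories with the strongest relationship and the greatest severity". Listing 16.2.3.1.1 shows every event with severity as a field.

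SAP 6.1 has a general convention that the number with missing values is shown where appropriate. The specific sentence in 6.4 overrides it for severity. The plan has no worst-case version of the severity table.

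**The concern.** Two of the three rules place an unknown where it counts against the drug. The third takes it out of the count, and the SAP gives no reason for the difference. The rule has two consequences:

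- The severe count can only move in the favourable direction.
- A child can appear in the TEAE tables but not in the matching severity table, so the two need not reconcile.

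Safety is part of the primary objective in both documents, and the trial population is children aged 6 to 12. If severe events are few, a small number of ungraded ones could be visible in an arm's percentage. A footnote reports such events but does not put them into that percentage.

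**Working it through.** The plan states no figure on this point, so there is nothing to reproduce. The check traces single children through the rules and then bounds the count.

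**Three cases within one preferred term**

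1. The only event is ungraded. The child is counted in the TEAE tables (14.3.1.2.x, 14.3.1.3.x) but is absent from 14.3.1.5.x. The totals differ by one.
2. One event is mild and one ungraded. The child is shown as mild. The totals agree, but the true greatest severity is unknown.
3. One event is severe and one ungraded. The child is shown as severe. The rule has no effect.

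**Bound on the severe count**

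Let S be the children in an arm with a recorded severe event. Let k be the other children in that arm with at least one ungraded event.

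- Count shown = S.
- True count lies between S (no ungraded event was severe) and S + k (each of the k children had an ungraded event that was severe).
- Shortfall lies between 0 and k, so the rule cannot produce an overcount.

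**What one child is worth**

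The ceiling on the shortfall in an arm's percentage is 100 × k / N. Protocol 6.10 gives 330 randomized 1:1:1, so N = 330/3 = 110. SAP 3.5 gives N = 153. Each ungraded child is then worth at most 100 × 1/110 = 0.91 points or 100 × 1/153 = 0.65 points.

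Neither S nor k is in the documents. The table below is an illustration with S = 5 and several values of k, all assumed:

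| k | N = 110: shown, ceiling | Largest shortfall | N = 153: shown, ceiling | Largest shortfall |
|---|---|---|---|---|
| 0 | 4.55%, 4.55% | 0 | 3.27%, 3.27% | 0 |
| 1 | 4.55%, 5.45% | 0.91 | 3.27%, 3.92% | 0.65 |
| 3 | 4.55%, 7.27% | 2.73 | 3.27%, 5.23% | 1.96 |
| 5 | 4.55%, 9.09% | 4.55 | 3.27%, 6.54% | 3.27 |

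These are arithmetic ceilings and do not estimate what the trial will show. They take every randomized child in the arm as the denominator. SAP 6.1 also says that subjects with missing values leave the denominator. If that were applied here, the percentages would change, but the bound on the count would not.

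**The case against.** The other side has a good deal to say, and most of it stands.

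- **The rule is pre-specified and disclosed.** The events are footnoted and listed. On the natural reading they still count in the TEAE, drug-related, serious, common-event, discontinuation and special-interest tables, none of which depends on the grade. A reader might infer that the events vanish from the safety report, and the documents do not support that. The sentence does refer to a single unnumbered table, so the reach has to be inferred. The shells in SAP Appendix 3 are not in the available text, so it cannot be said whether the footnote would give counts by arm.
- **Missing grades should be rare.** Protocol 5.4.1.2 and 5.4.1.3 require the investigator to grade every event. Protocol 7.4.3 and SAP 8 provide for checks and queries.
- **There is no breach of the greatest-severity rule.** A reader might see a contradiction when a child with one mild and one ungraded event is shown as mild. Mild is the greatest recorded grade, so the rule in 7.8.1 is being followed.
- **Differential loss is not documented.** A reader might suppose that grades go missing mainly in early withdrawals and unequally by arm. Nothing in the documents says so, and Protocol 4.6 has children who discontinue early complete Visit 7, where adverse events are collected.
- **Worst-case counting has its own bias.** Setting every ungraded event to severe labels it "Incapacitating with inability to do usual activities or significantly affects clinical status and warrants intervention" (Protocol 5.4.1.3) without an investigator's judgment, and that can only overcount.

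The last item is a reason to show the worst case beside the main count and not in its place. None of these arguments changes the direction of the rule or the possible mismatch of totals.

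**Conclusion.** The point holds as a minor one. Because of the severity rule in SAP 6.4, the severe count can be exact or too low but never too high, and the severity tables may not reconcile with the TEAE tables. The same paragraph handles the other two unknowns conservatively.

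A reader might infer that severe events will be undercounted, or that the loss could rival the severe rate itself. Neither is supported. If no ungraded event was severe, the count is exact. If no grade is missing after queries, the rule does nothing. The size cannot be computed from the documents, which give no severe-event rate and no missingness rate.

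The conclusion assumes that the sentence refers to the severity tables and extends to the severe line of Table 14.3.1.1. If it were read as covering all adverse event summaries, the loss would be wider, which is one more reason to name the tables.

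**What to change.** Replace the sentence in SAP 6.4 with:

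*TEAEs with missing severity will be kept in Tables 14.3.1.5.1 to 14.3.1.5.3 in a 'severity not reported' row by arm, so that totals equal the TEAE tables. The severe TEAE count in Tables 14.3.1.1 and 14.3.1.5.x will also be shown with missing severity counted as severe, consistent with the rule for missing relationship.*

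It would help to add that a child with a graded and an ungraded event of the same preferred term stays at the recorded grade in the main display and moves to severe only in the worst-case version.

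The cost is this SAP wording and minor programming before database lock, one extra row, and possibly a slightly higher severe count in the worst-case version. If every grade is complete after queries, no result changes.

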6.5.6 Adaptation Rules

Based on the conditional power calculated in Section 6.5.5, the independent statistician will use the following adaptation rules for sample size adjustment and make recommendation to the sponsor.

Table 2. Sample Size Adjustment Decision Rules

| Case | Dose 1 (█ mg) | Dose 2 (█ mg) | Decision for Stage 2 Sample Size Adjustment | Verbiage for Communication to Sponsor (Section 6.5.8) |
|------|---|---|--|--|
| 1 | $Cp_L < 10\%$ | $CP_H < 10\%$ | Terminate the trial. | CASE 1. Terminate the trial. |
| 2 | $Cp_L < 10\%$ | $10\% \leq CP_H \leq 36\%$ or $CP_H > 80\%$ | Subjects to be randomized to Dose 1 group in Stage 2 will be allocated to Dose 2 and Placebo groups; However, subjects who received dose 1 prior to the interim analysis will continue to receive dose 1 in Stage 2. | CASE 2. Stop enrollment for █ mg group, allocate Stage 2 planned █ mg sample size to █ mg and Placebo. |
| 3 | $10\% \leq CP_L \leq 36\%$ or $CP_L > 80\%$ | $CP_H < 10\%$ | Subjects to be randomized to Dose 2 group in Stage 2 will be allocated to Dose 1 and Placebo groups; However, subjects who received Dose 2 prior to the interim analysis will continue to receive Dose 2 in Stage 2. | CASE 3. Stop enrollment for █ mg group, allocate Stage 2 planned █ mg sample size to █ mg and Placebo. |
| 4 | $Cp_L < 10\%$ | $36\% < CP_H \leq 80\%$ | 
Enrollment for Dose 1 group will be terminated. Sample size in Dose 2 and Placebo groups will be increased to achieve the conditional power of at least 90% (before the multiplicity adjustment). This increase will include subjects allocated to Dose 2 and Placebo from Dose 1 termination
 
The maximum increase will not result in the doubling of the total sample size. In other words, suppose n_1 and n_2 are the sample sizes per arm at the interim analysis and n_{2adj} is the calculated adjusted sample size. If $(n_1 + n_{2adj}) \leq 2 * (n_1 + n_2)$ then the adjusted sample size for Stage 2 will be n_{2adj} as calculated. If $((n_1 + n_{2adj}) > 2 * (n_1 + n_2))$ then $n_{2adj} = 2 * (n_1 + n_2) - n_1$.
 | CASE 4. Stop enrollment for █ mg group, increase Stage 2 sample sizes for █ mg and Placebo to xxx/group. |

| Case | Dose 1 (█ mg) | Dose 2 █ mg) | Decision for Stage 2 Sample Size Adjustment | Verbiage for Communication to Sponsor (Section 6.5.8) |
|------|--|--|---|--|
| 5 | 36%<CP _L ≤80% | Cp _H <10% | 
Enrollment for Dose 2 group will be terminated. Sample size in Dose 1 and Placebo groups will be increased to achieve the conditional power of at least 90% (before the multiplicity adjustment). This increase will include subjects allocated to Dose 1 and Placebo from Dose 2 termination.
 
The maximum increase will not result in the doubling of the total sample size.
 | CASE 5. Stop enrollment for █ mg group, increase Stage 2 sample sizes for █ mg and Placebo to xxx/group. |
| 6 | 10%≤CP _L ≤36% or CP _L >80% | 10%≤CP _H ≤36% or CP _H >80% | Retain the original sample sizes of each treatment group. | CASE 6. No change in sample sizes. |
| 7 | 36%<CP _L ≤80% | 36%<CP _H ≤80% | 
Increase the sample size in all treatment groups to achieve the conditional power of at least 90% (before the multiplicity adjustment) in both treatment groups.
 
The maximum increase will not result in the doubling of the total sample size.
 | CASE 7. Increase Stage 2 sample sizes for █ mg to xxx █ mg to xxx, and Placebo to xxx. |
| 8 | 10%≤CP _L ≤36% or CP _L >80% | 36%<CP _H ≤80% | 
Retain the original sample size in Dose 1 group and increase the sample size in Dose 2 and Placebo groups to achieve the conditional power of at least 90% (before the multiplicity adjustment).
 
The maximum increase will not result in the doubling of the total sample size.
 | CASE 8. Increase Stage 2 sample sizes for █ mg and Placebo to xxx/group. |

| Case | Dose 1 (█ mg) | Dose 2 █ mg) | Decision for Stage 2 Sample Size Adjustment | Verbiage for Communication to Sponsor (Section 6.5.8) |
|------|--------------------------|--|--|---|
| 9 | 36%<CP _L ≤80% | 10%≤CP _H ≤36% or CP _H >80% | Retain the original sample size in Dose 2 group and increase the sample size in Dose 1 and Placebo groups to achieve the conditional power of at least 90% (before the multiplicity adjustment). The maximum increase will not result in the doubling of the total sample size. | CASE 9. Increase Stage 2 sample sizes for █ and Placebo to xxx/group. |

Note the sample size to achieve the conditional power of CP=90% is calculated as follows (Chang 2008a and 2008b, Hintze 2013, and Jennison and Turnbull 2000),

$$n_2 = \frac{2\sigma^2}{\delta^2} \left\{ \frac{1}{\sqrt{w_2}} (Z_{1-\alpha_2} - \sqrt{w_1} Z_{1-p_1}) - \Phi^{-1}(1 - CP) \right\}^2,$$

$$= \frac{n_1}{Z_{1-p_1}^2} \left\{ \frac{1}{\sqrt{w_2}} (Z_{1-\alpha_2} - \sqrt{w_1} Z_{1-p_1}) - \Phi^{-1}(1 - CP) \right\}^2.$$

The following rules will be applied to compute the sample sizes across the treatment arms in Stage 2:

- If a decision to discontinue subject enrollment is made for a particular dosing arm at Interim Analysis, subjects who were planned to be enrolled in that arm after Interim Analysis will be re-distributed to the remaining treatment arms. For example, if Dose 1 is dropped and Dose 2 is retained, the sample sizes for the three treatment arms in Stage 2 will be defined as follows:
 - Dose 1: 0
 - Dose 2: $n_{22} + n_{21} / 2$
 - Placebo: $n_{23} + n_{21} / 2$

where n_{ij} is the sample size allocated to Stage i for Treatment Group j .

- If a decision is made to increase the sample size in at least one dosing arm, the modified sample size in the placebo arm will be equal to the larger modified sample size in the two dosing arms. For example, if the modified sample sizes in the two dosing arms in Stage 2 are n_{31} and n_{32} , respectively, the modified sample size in the placebo arm in Stage 2 will be set to $\max(n_{31}, n_{32})$. However, if the sample size is increased in one dosing arm, the sample size in the other dosing arm will not be automatically increased.

6.5.7 Adaptive Design

This section defines the mathematical approach used in the proposed adaptive design with two stages and data-driven decision rules (e.g., sample size modification at Interim Analysis). The derivation of the adaptive design is based on the combination function approach applied in conjunction with the closure principle, see, for example, Wang et al. (2001), Brannath et al. (2002) and Hommel (2005). This general approach is commonly used to construct adaptive designs in confirmatory trials and guarantees that the overall Type I error rate is protected in the trial at the nominal level (two-sided $\alpha = 0.05$) regardless of the type of design modifications at an Interim Analysis, including decisions to drop a treatment arm or adjust the sample size in one or more arms.

Let H_1 and H_2 denote the null hypotheses of no treatment effect for the two dose-placebo comparisons (Dose 1 versus placebo and Dose 2 versus placebo). According to the combination function approach, the amount of evidence to reject these null hypotheses will be evaluated separately in each individual stage of the trial and the inferences at the final analysis will be performed by combining the evidence across the two stages. Further, the rejection rules for H_1 and H_2 will be chosen to achieve consistency with the Hochberg procedure (Dmitrienko and D'Agostino, 2013) that was pre-defined as multiplicity adjustment tool in this trial. To achieve this consistency, the Hochberg procedure will be applied within each stage (Hochberg, 1988).

Let p_i and q_i denote the p-values for testing the null hypothesis H_i , $i = 1, 2$, based on the data in Stages 1 and 2, respectively. The Stage 2 p-values are computed from the samples obtained after Interim Analysis, i.e., the sample size in a dosing arm may be adjusted as explained above. Further, $p_{(1)} < p_{(2)}$ will denote the ordered treatment effect p-values in Stage 1 and similarly $q_{(1)} < q_{(2)}$ will denote the ordered treatment effect p-values in Stage 2. These p-values will be used to construct a closure-based representation of the Hochberg procedure in each of the two stages. To define the closure-based representation, a closed family of intersection hypotheses that includes all possible non-empty intersections of the two null hypotheses will be set up. Table 3 and Table 4 display the intersection hypotheses in the closed family and associated intersection p-values that define the Hochberg procedure in Stage 1 and Stage 2 respectively.

Table 3: Intersection hypothesis and Hochberg intersection p-values in Stage 1

| Intersection hypothesis | Hochberg intersection p-value |
|-------------------------|--------------------------------------|
| $H_1 \cap H_2$ | $p_{12} = \min (2 p_{(1)}, p_{(2)})$ |
| H_1 | p_1 |
| H_2 | p_2 |

Table 4: Intersection hypothesis and Hochberg intersection p-values in Stage 2

| Intersection hypothesis | Hochberg intersection p-value |
|-------------------------|--------------------------------------|
| $H_1 \cap H_2$ | $q_{12} = \min (2 q_{(1)}, q_{(2)})$ |
| H_1 | q_1 |
| H_2 | q_2 |

Note that, if a certain dose is dropped due to futility at Interim Analysis, the corresponding p-values in Stage 2 is automatically set to 1 to remove the dosing arm from consideration. This guarantees that a null hypothesis cannot be rejected at Final Analysis if the corresponding dose was dropped due to futility at Interim Analysis. Further, the p-values computed at Interim Analysis (Stage 1 p-values) are not used for inferential purposes and therefore no α will be spent at Interim Analysis to stop the trial early due to overwhelming efficacy.

As an illustration, if Dose 1 is dropped at Interim Analysis, the corresponding treatment effect p-value in Stage 2 (q_1) will be set to 1. As a result, the intersection p-values will be defined in Stage 2 as shown in Table 5 (note that the smaller ordered p-value will be equal to q_2 and the larger ordered p-value will be equal to 1).

Table 5: Intersection hypotheses and Hochberg intersection p-values in Stage 2 if dose 1 is dropped at Interim Analysis

| Intersection hypothesis | Hochberg intersection p-value |
|-------------------------|-------------------------------|
| $H_1 \cap H_2$ | $q_{12} = \min(2 q_2, 1)$ |
| H_1 | 1 |
| H_2 | q_2 |

The inferences for the two null hypotheses will be performed at final analysis using the composite treatment effect p-values that will be defined as follows. Let w_1 and w_2 define the stage weights that are prospectively defined based on the expected amount of information at Interim Analysis. Since Interim Analysis is planned to be taken after 50% of the subjects have completed the trial, n_1 (total sample size in Stage 1) and n_2 (total sample size in Stage 2 before sample size adjustment), and thus the pre-specified stage weights are given by

$$w_1 = \frac{n_1}{n_1 + n_2} = 0.5, w_2 = \frac{n_2}{n_1 + n_2} = 0.5.$$

Using the stage weights, the combination function to be used at Final Analysis will be defined as follows:

$$c(x_1, x_2) = 1 - \Phi[\sqrt{w_1}\Phi^{-1}(1 - x_1) + \sqrt{w_2}\Phi^{-1}(1 - x_2)],$$

where $\Phi(x)$ is the cumulative distribution function of the standard normal distribution.

This combination function will be applied to compute composite intersection p-values for each intersection hypothesis in the closed family. The resulting composite intersection p-values are denoted by r_{12} , r_1 , r_2 , and are defined in Table 6.

Table 6: Intersection hypothesis and composite intersection p-values at final analysis

| Intersection hypothesis | Composite intersection p-value |
|-------------------------|--------------------------------|
| $H_1 \cap H_2$ | $r_{12} = c(p_{12}, q_{12})$ |
| H_1 | $r_1 = c(p_1, q_1)$ |
| H_2 | $r_2 = c(p_2, q_2)$ |

After that, the null hypothesis H_1 will be rejected at Final Analysis (which implies a statistically significant treatment effect at Dose 1) if the composite p-values for all intersection hypotheses in the closed family that contain H_1 are significant at $\alpha = 0.05$ (two-sided), i.e.,

$$r_{12} \leq \alpha \text{ and } r_1 \leq \alpha.$$

Similarly, the null hypothesis H_2 will be rejected at Final Analysis (and a statistically significant treatment effect will be established at Dose 2) if the composite p-values for all intersection hypotheses in the closed family that contain H_2 are significant at $\alpha = 0.05$, i.e.,

$$r_{12} \leq \alpha \text{ and } r_2 \leq \alpha.$$

As indicated above, the resulting approach accounts for two sources of multiplicity in this clinical trial (multiple data looks and multiple dose-placebo comparisons) and guarantees Type I error rate control at $\alpha = 0.05$. The α control is retained even if the sample size is adjusted in one or more treatment arms at Interim Analysis. In addition, it needs to be emphasized that a null hypothesis cannot be rejected at Final Analysis if the corresponding dose was dropped due to futility at Interim Analysis.

6.5.8 *Communication of the Interim Analysis Results to the Trial Sponsor*

The recommendation will be made to the sponsor Executive VP and Chief Medical Officer for Clinical Development and Senior Director of Biostatistics at Supernus in a formal password protected letter. The verbiage for the letter will be:

Based on the conditional power calculation for the diary data at the cutoff date (DDMMYY) and the pre-specified adaptation rules as documented in the Interim Analysis Plan, a recommendation is made for study 810P301 to the effect that:

'terminate the trial' or 'stop enrollment for [REDACTED] mg group or allocate Stage 2 planned [REDACTED] mg sample size to [REDACTED] mg and Placebo' or 'stop enrollment for [REDACTED] mg group, allocate Stage 2 planned [REDACTED] mg sample size to [REDACTED] mg and Placebo' or 'stop enrollment for [REDACTED] mg group, increase Stage 2 sample sizes for [REDACTED] mg and Placebo to xxx/group' or 'stop enrollment for [REDACTED] mg group, increase Stage 2 sample sizes for [REDACTED] mg and Placebo to xxx/group' or 'no change in sample sizes' or 'increase Stage 2 sample sizes for [REDACTED] mg to xxx [REDACTED] mg to xxx, and Placebo to xxx' or 'increase Stage 2 sample sizes for [REDACTED] mg and Placebo to xxx/group' or 'increase Stage 2 sample sizes for [REDACTED] mg and Placebo to xxx/group.'

To protect the trial integrity, no other information will be provided in the letter or in any other communication.

6.6 *Timing of Final Analyses*

Data summary and statistical analysis will commence after all subjects have completed study Visit 7 (or discontinued prior to Visit 7) and the study database is cleaned and locked.

6.7 *Multicenter Study*

This is a multicenter study. The primary analysis will have all sites pooled. Where applicable, analysis adjusting for site effect or analysis evaluating homogeneity across sites may be carried out. If conducted, small sites (defined as those with sample size <9 ITT subjects/site) will be pooled with larger sites based on the geographic proximity.

6.8 *Multiple Comparisons/Multiplicity Adjustment*

With respect to the primary endpoint, the details of this multiplicity adjustment in the context of the adaptive design employed in this trial are defined in Sections 6.5.7. Multiplicity adjustment for secondary endpoints is described in Section 7.7.7.

6.9 *Examination of Subgroups*

In addition to the analysis adjusted for the confounding effects by the covariates (see Section 6.3), primary and key secondary efficacy variables will be summarized by subgroup to explore the heterogeneity of the treatment effect across subgroups. Subgroups are defined as follows:

- Gender (Male, Female)
- Age (6-9, 10-12)
- Race (White, Black/African American, Other)

